6.2.2. Day 1 Assessments

The following assessments are to be completed at the Day 1 visit. The Investigator must have received the results from the screening assessments before proceeding with the visit. Subjects must complete all Day 1 procedures before being dispensed the study drugs. Initiation of treatment with HIV study drugs must take place within 24 hours after the Day 1 visit.

- Review AEs and changes in concomitant medications
- Complete physical examination (urogenital/anorectal exams will be performed at the discretion of the Investigator)
- Obtain vital signs, including weight
- Obtain urine samples for the following laboratory analyses:
 - Urinalysis and urine chemistry
 - Urine pregnancy test (females of childbearing potential only). If the urine pregnancy test is positive at Day 1, study drugs will not be dispensed. The positive result will be confirmed with a serum pregnancy test. If the serum pregnancy test is positive, the subject will not be able to participate.

- Renal tubular function assessments (collected fasted, no food or drink, except water, at least 8 hours prior to blood collection): retinol binding protein, beta-2 microglobulin, urine albumin, and urine protein
- Urine sample storage for possible additional clinical testing
- Obtain blood samples for the following laboratory analyses:
 - Chemistry profile
 - Hematology profile
 - Coagulation assessments
 - Metabolic assessments (collected fasted, no food or drink, except water, at least 8 hours prior to blood collection): glucose and lipid panel (total cholesterol, HDL, direct LDL, and triglycerides).
 - If the subject has not fasted prior to the visit, the visit may proceed, but the subject must return within 72 hours in a fasted state to draw blood for the metabolic assessments.
 - CD4+ cell count
 - Plasma HIV-1 RNA
 - Plasma HCV RNA
 - Serum bone safety assessments: (collected fasted, no food or drink, except water, at least 8 hours prior to blood collection) parathyroid hormone (PTH) and serum 25-OH Vitamin D
 - If the subject has not fasted prior to the visit, the visit may proceed, but the subject must return within 72 hours in a fasted state to draw blood for these assessments.
 - Platelet and coagulation function assessments may include: Soluble glycoprotein VI (sGPVI), P-selectin, soluble CD40 ligand, and D-dimer
 - Inflammation assessments may include: cystatin-C, IL 6, hs CRP, sCD14, sCD163, sTNF-R1, and Lp-PLA2
 - Plasma storage samples for virology, safety, and/or PK testing
 - Serum storage sample for possible additional clinical testing

- Obtain estimated glomerular filtration rate according to the Cockcroft-Gault formula (see Section 4.2 for details)
- Complete questionnaires: subject is to read questionnaire by her/himself and write/mark answers directly onto the questionnaires.
 - Adherence for HIV (VAS)
 - HIV Treatment Satisfaction Questionnaire Status version (HIVTSQs)
 - Medical Outcomes Short Form-36 (SF-36)
 - Functional Assessment of Chronic Illness Therapy-Fatigue scale (FACIT-F)
 - Chronic Liver Disease Questionnaire (CLDQ-HCV)
 - Work Productivity and Activity Impairment Questionnaire: Hepatitis C, v2.0 (WPAI: Hepatitis C)

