5. INVESTIGATIONAL MEDICINAL PRODUCTS

5.1. Randomization

Subjects will be assigned a screening number at the time of consent. Once eligibility has been confirmed, each subject will be assigned a unique subject number. Once a subject number has been assigned to a subject, it will not be reassigned to any other subject. Prior to or during the Day 1 visit, the Investigator or designee will randomize the subject using the Interactive Web Response System (IWRS). The subject number assignment and randomization may be performed up to 7 days prior to the in-clinic Day 1 visit provided that all screening procedures have been completed and subject eligibility has been confirmed.

Subjects will be randomized in a 1:1 ratio to one of the following two treatment arms:

Treatment Arm 1: Switch from 2 NRTI plus a third ARV agent to E/C/F/TAF FDC (n = 60)

Treatment Arm 2: Switch from 2 NRTI plus a third ARV agent to F/R/TAF FDC (n = 60)

Randomization will be stratified by race (black vs. non-black).

The IWRS will assign study drug bottle numbers to be dispensed to the subject at each study visit, for all HIV and HCV study drugs. **All Day 1 assessments and procedures must be completed prior to the administration of the first dose of HIV study drug**. Initiation of treatment with the HIV study drug must take place within 24 hours after the Day 1 visit.

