6.3. Randomization

- Obtain subject number and randomize the subject via the IWRS. The subject number assignment and randomization may be performed up to 7 days prior to the in-clinic Day 1 visit provided that all screening procedures have been completed and subject eligibility has been confirmed.
- **Dispense HIV study drugs**. Subjects should initiate dosing of HIV study drugs after Day 1 visit assessments. Initiation of treatment with the study drugs must take place within 24 hours after the Day 1 visit.
 - Subjects should also be counseled regarding the importance of adherence and taking their study drug daily with food at approximately the same time each day.

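### A fasted redraw 24 to 72 hours after an unfasted Day 1 visit cannot fit the first-dose rules; if the dose is taken first, the fasting lipid baseline, and usually the fasting glucose baseline, can be lost (minor)

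*Protocol*

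**What the plan says.** **Redraw.** Protocol 6.2.2 lists fasting glucose and lipids, and the fasting bone markers, among the Day 1 blood samples. For an unfasted subject, the metabolic line reads "the visit may proceed, but the subject must return within 72 hours in a fasted state to draw blood for the metabolic assessments". The bone line says likewise that "the subject must return within 72 hours in a fasted state to draw blood for these assessments". Footnote o of Protocol Appendix 2, copied in SAP Appendix 1, repeats the 72 hours for the bone, renal, inflammation and platelet samples.

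**Order.** Protocol 6.2.2: "Subjects must complete all Day 1 procedures before being dispensed the study drugs". Protocol 5.1: "All Day 1 assessments and procedures must be completed prior to the administration of the first dose of HIV study drug". Appendix 2 footnote u also places dispensing after the Day 1 assessments.

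**Deadline.** Protocol 6.2.2: "Initiation of treatment with HIV study drugs must take place within 24 hours after the Day 1 visit". Sections 5.1 and 6.3 and Appendix 2 footnote b repeat it.

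**Analysis.**
- SAP 3.8.1 makes the first-dose date Study Day 1 and takes as baseline the last value on or before it.
- SAP Table 3-2 assigns fasting glucose and lipids from Study Day 2 to 98 to Week 8.
- SAP 7.3.1 summarizes only fasting metabolic values, and SAP 7.3.2 does not grade nonfasting lipids.
- Under Protocol 8.5.3 and SAP 7.3.2.1, if baseline is missing, any abnormality of Grade 1 or higher is treatment-emergent.
- SAP Appendix 4, item 12b, counts every graded post-baseline result, not only those at summarized visits.

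**The concern.** The protocol gives sites a 72-hour allowance, but the later part of it cannot be used without breaking either the order rule or the dosing deadline. No text says which gives way. A site may reasonably take the permission for the visit to proceed as permission to dispense and dose, with the fasted sample to follow. The SAP then treats the sample that was meant as the baseline as an on-treatment value.

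Safety of the switch is a secondary objective, and no arm stays on its previous regimen. Change from the subject's own baseline is therefore how a metabolic effect of switching would be seen. Lipids are a relevant signal: Protocol 1.2.2 reports larger cholesterol increases on E/C/F/TAF than on E/C/F/TDF in the Phase 2 study. A subject without a fasting baseline leaves the change-from-baseline summaries, and pre-existing abnormalities are counted as arising on study.

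**Working it through.** The plan gives no figure for this point, so the check compares the rules and then follows the dates.

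**1. Can the rules be met together?** Let *D* be the hours from the visit to the first dose and *R* the hours to the redraw. The rules are *D* ≤ 24, *R* before *D*, and *R* ≤ 72. The first two force *R* below 24. The first 24 hours of the allowance are therefore usable, and the remaining 72 − 24 = 48 hours are not.

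**2. Where does a late redraw land if the dose comes first?** Study Day = redraw date − first-dose date + 1 (SAP 3.8.1). Count dates from the visit: the first dose is on date 0 or 1, and a redraw at 24 to 72 hours is on date 1, 2 or 3.

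| First dose | Redraw date 1 | Redraw date 2 | Redraw date 3 |
|---|---|---|---|
| Date 0 | Study Day 2 | Study Day 3 | Study Day 4 |
| Date 1 | Study Day 1 | Study Day 2 | Study Day 3 |

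Baseline needs Study Day 1 or earlier. Five of the six cells fall in the Week 8 window [2, 98]. The sixth is accepted as baseline by date although it follows the first dose.

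**3. Is there another baseline value?**
- *Lipids:* none. Screening (Protocol 6.2.1) has no lipid panel, and an unfasted Day 1 lipid value is not used.
- *Glucose:* Appendix 2 footnote h moves Day 1 glucose into the fasting panel, and SAP 7.3.2.1 says nonfasting glucose was not assessed at Study Baseline. Screening chemistry does include glucose, with no fasting requirement. If that sample happened to be fasted, it could serve.

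**4. What follows in the tables?** Change from Study Baseline is missing. For Part 1 and Whole Study, any graded fasting value counts as treatment-emergent, including the redraw itself. In Protocol Appendix 4 grading starts at 130 mg/dL for adult fasting LDL, 200 mg/dL for cholesterol, 110 mg/dL for fasting glucose and 500 mg/dL for triglycerides. Co-administration uses the Part 2 Baseline, for which a fasted Week 8 sample taken by the first LDV/SOF date serves. By-visit Week 8 values change little, because SAP 3.8.3 takes the record closest to Day 56.

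**5. Size per affected subject, for one test.** The SAP 7.3.2.2 denominator is subjects with a post-baseline value.

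| Share with post-baseline values | Per arm | Overall |
|---|---|---|
| All | 1/60 = 1.7 points | 1/120 = 0.8 points |
| 90% (assumed) | 1/54 = 1.9 points | 1/108 = 0.9 points |
| 80% (assumed) | 1/48 = 2.1 points | 1/96 = 1.0 points |

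One added count is a ceiling. A subject whose grade rises after the switch would be counted even with a baseline, and a subject with no graded value after the first dose is not counted at all.

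**6. With the redraw before the dose and within 24 hours.** The redraw date is then no later than the first-dose date. It falls on Study Day 1, or on Study Day −1 if drawn on the visit date with the dose the next day. Both meet the baseline rule.

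**The case against.** The strongest reply is that 72 hours is only a ceiling. A fasted return the next morning satisfies every rule. The assessments-first order is stated in 5.1, in 6.2.2 and in footnote u, and no text authorizes dosing before the redraw. The loss of baseline therefore needs either a breach of that order or a particular reading of the permission to proceed. This stands, and it makes the point a request for clarification. It does not remove the point, because a site using hours 24 to 72 as written must break one rule or the other.

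It is also fair that the missing-baseline rule is prespecified and over-counts abnormalities rather than hiding them. That is why the rule should stay as it is.

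Some stronger readings are not supported:
- *Every unfasted subject loses the baseline.* An early redraw before dosing keeps it.
- *Five in six late redraws are lost.* The six cells are calendar cases, not probabilities.
- *Bone and tubular markers lose their baseline too.* The SAP sets no fasting restriction on them, so a pre-dose sample drawn unfasted at the visit would serve. They are exposed only if no such sample is taken.

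**Conclusion.** The inconsistency is real but minor. A redraw at 24 to 72 hours cannot meet both the order rule and the 24-hour dosing limit. If dosing goes first and the redraw falls on Study Day 2 to 4, the subject has no fasting lipid baseline, and no fasting glucose baseline unless the Screening glucose was fasted.

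The effect is at most one extra treatment-emergent count per test for each affected subject with a pre-existing graded value. That is at most about 1.7 percentage points of an arm if all 60 have post-baseline values. The documents do not say how many subjects would arrive unfasted, return late and be dosed first; the number may be zero.

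A reader might infer a threat to the trial's efficacy conclusions. The documents do not support that: SVR12, SVR4 and the HIV endpoints do not use these samples, and SAP 7.3 plans no inferential statistics on laboratory data.

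**What to change.** State that at Day 1 the fasted redraw must be taken before the first dose of HIV study drug and within the existing 24-hour limit, with drug dispensed at that return. Four short edits do this: both 72-hour lines in Protocol 6.2.2, footnote o of Protocol Appendix 2, and its copy in SAP Appendix 1. In footnote o, limit the change to Day 1, because the footnote also serves later visits.

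Footnote b naturally means that only HIV drug, not LDV/SOF, is dispensed on Day 1. It needs an edit only if it is read as barring dispensing at the return visit.

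The cost is a shorter redraw window. A subject who cannot return fasted within 24 hours may still lack a fasting baseline. The dosing deadline, visit windows and SAP rules do not move.

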6.3. Randomization

- Obtain subject number and randomize the subject via the IWRS. The subject number assignment and randomization may be performed up to 7 days prior to the in-clinic Day 1 visit provided that all screening procedures have been completed and subject eligibility has been confirmed.
- **Dispense HIV study drugs**. Subjects should initiate dosing of HIV study drugs after Day 1 visit assessments. Initiation of treatment with the study drugs must take place within 24 hours after the Day 1 visit.
 - Subjects should also be counseled regarding the importance of adherence and taking their study drug daily with food at approximately the same time each day.

6.4. Treatment Assessments

6.4.1. HIV and HCV Treatment Visits (Weeks 4, 6, 8, 12, 16, and 20)

The following assessments are to be completed at the end of Weeks 4, 8, 12, 16, and 20, unless otherwise specified. The Week 6 visit is a laboratory visit only – please see Section 6.4.1.1 for details.

All study visits are to be scheduled relative to the Day 1 visit date. Study visits are to be completed within ± 2 days of the protocol-specified visit date based on the Day 1 visit through Week 20.

- Review AEs and changes in concomitant medications
- Perform symptom-directed physical examination as needed

- Obtain vital signs, including weight
- Obtain urine samples for the following laboratory analyses:
 - Urinalysis and urine chemistry
 - Urine pregnancy test (females of childbearing potential only); positive urine pregnancy
 tests will be confirmed with a serum test. If the serum test is positive, the subject will be
 discontinued.
 - Renal tubular function assessments (Weeks 4, 8, 12, and 20 only)
 - Urine sample storage for possible additional clinical testing
- Obtain blood samples for the following laboratory analyses:
 - Chemistry profile
 - Hematology profile
 - Coagulation assessments
 - Metabolic assessments (Weeks 8 and 20 only)
 - CD4+ cell count
 - Plasma HIV-1 RNA
 - Plasma HCV RNA (Weeks 8, 12, 16, and 20 only)
 - Samples for population PK (Weeks 4, 8, 12, 16, and 20)
 - Two (2) blood samples will be collected: 1) the predose sample should be drawn prior to observed study drug dosing; 2) the postdose sample should be drawn between 15 mins and 4 hours postdose.
 - Serum bone safety assessments (Weeks 4, 8, 12, and 20 only)
 - Platelet and coagulation function assessments (Weeks 4, 8, 12, and 20 only)
 - Inflammation assessments (Weeks 4, 8, 12, and 20 only)
 - Plasma storage samples for virology, safety, and/or PK testing
 - Serum storage sample for possible additional clinical testing

- Obtain estimated glomerular filtration rate according to the Cockcroft-Gault formula (see Section 4.2 for details)
- Complete questionnaires (Weeks 8 and 20 only): subject is to read questionnaire by her/himself and write/mark answers directly onto the questionnaires.
 - VAS for HIV adherence
 - HIVTSQc Change version
 - SF-36
 - FACIT-F
 - CLDQ-HCV
 - WPAI: Hepatitis C
- Subjects who meet the criteria for virologic rebound should be managed according to Management of HIV Virologic Failure (Section 6.9)
- Document study drugs dispensation and accountability for all study drugs dispensed. Counsel all subjects regarding the importance of adherence and maintaining consistency to study drug administration.
 - HIV study drugs are dispensed at every visit (with the exception of Week 6 laboratory visit).
 - HCV treatment will commence at Week 8, after determination of HIV suppression (< 50 copies/mL) based on the Week 6 HIV-1 RNA value and tolerability of HIV study drugs. Once confirmed, dispense HCV study drug (LDV/SOF) at Weeks 8, 12, and 16 only.
- 6.4.1.1. Week 6 (Laboratory Visit Only)

The Week 6 visit is a laboratory visit only, to confirm HIV suppression prior to initiation of HCV treatment.

The following will be performed and documented at the Week 6 visit:

- Obtain blood samples for plasma HIV-1 RNA testing
- Plasma storage sample for safety and virology testing

6.4.2. HIV Treatment and Post-HCV Treatment Assessments (Post-HCV Treatment Weeks 4 and 12)

The following evaluations are to be completed at the end of 4 and 12 weeks after completion of HCV treatment (Post-HCV Treatment Weeks 4 and 12 visits, respectively) and should be timed from the date of last administration of the HCV treatment. The Post-HCV Treatment Week 4 visit is to be completed \pm 2 days, and the Post-HCV Treatment Week 12 visit is to be completed within \pm 4 days; however, unless notified by Gilead Sciences, the Post-HCV Treatment Week 4 and 12 should be completed within 2 and 4 days of the protocol-specified visit date, respectively.

All subjects must complete the Post-HCV Treatment Weeks 4 and 12 visits. The end of study will occur at the Post-HCV Treatment Week 12 visit.

The following assessments are to be completed:

- Review AEs and changes in concomitant medications
- Complete physical examination (**Post-HCV Treatment Week 12 only**) (urogenital/anorectal exams will be performed at the discretion of the Investigator)
- Perform symptom-directed physical examination as needed
- Obtain vital signs, including weight
- Obtain urine samples for the following laboratory analyses:
 - Urinalysis and urine chemistry
 - Urine pregnancy test (females of childbearing potential only); positive urine pregnancy tests will be confirmed with a serum test. If the serum test is positive, the subject will be discontinued.
 - Renal tubular function assessments (Post-HCV Treatment Week 12 only)
 - Urine sample storage for possible additional clinical testing
- Obtain blood samples for the following laboratory analyses:
 - Chemistry profile
 - Hematology profile
 - Coagulation assessments
 - Metabolic assessments (Post-HCV Treatment Week 12 only)

- CD4+ cell count
- Plasma HIV-1 RNA
- Plasma HCV RNA
- Serum bone safety assessments (Post-HCV Treatment Week 12 only)
- Platelet and coagulation function assessments (Post-HCV Treatment Week 12 only)
- Inflammation assessments (Post-HCV Treatment Week 12 only)
- Plasma storage samples for virology, safety, and/or PK testing
- Serum storage sample for possible additional clinical testing

- PPD

- Obtain estimated glomerular filtration rate according to the Cockcroft-Gault formula (see Section 4.2 for details)
- Complete questionnaires (Post-HCV Treatment Week 12 only): subject is to read questionnaire by her/himself and write/mark answers directly onto the questionnaires.
 - VAS for HIV adherence
 - HIVTSQc Change version
 - SF-36
 - FACIT-F
 - CLDQ-HCV
 - WPAI: Hepatitis C
- Subjects who meet the criteria for virologic rebound should be managed according to Management of HIV Virologic Failure (Section 6.9)
- Document study drugs dispensation and accountability for all **HIV** study drugs dispensed. Counsel all subjects regarding the importance of adherence and maintaining consistency to HIV study drug administration.

6.5. Post-treatment Assessments

6.5.1. Early Study Drug Discontinuation (ESDD) Visit

Early study drug discontinuation during Part 1 (Day 1 through Week 8):

If the subject discontinues HIV study drug dosing in Part 1, the subject will be discontinued from the study and will not continue to Part 2 of the study. The subject will be asked to return to the clinic within 72 hours of stopping HIV study drugs for the ESDD visit, followed by the 30-Day Follow-Up visit.

Early study drug discontinuation during Part 2 (after initiation of HCV treatment):

If the subject discontinues HCV study drug dosing only prior to completing the 12-week HCV treatment, the following will occur:

- Be asked to return to the clinic within 72 hours of stopping HCV study drug for the ESDD visit.
- Remain in the study to return for follow-up visits 4 and 12 weeks after the last dose of LDV/SOF, as described in Section 6.4.2.
- Continue to receive HIV study drugs (see ESDD procedures below).

If the subject discontinues HIV study drug dosing only, the following will occur:

- Be asked to return to the clinic within 72 hours of stopping HIV study drugs for the ESDD visit.
- HIV regimen may be changed, after discussion with the Medical Monitor. The new HIV regimen should be designed to allow continued dosing of LDV/SOF. LDV/SOF should be continued unless an HIV regimen cannot be constructed that would allow coadministration with the new HIV regimen.
- Remain in the study to complete the 12-week HCV treatment (see Section 6.4.1) and follow-up visits 4 and 12 weeks after the last dose of LDV/SOF, as described in Section 6.4.2.

If the subject discontinues both HIV and HCV study drug dosing, the following will occur:

- Be asked to return to the clinic within 72 hours of stopping study drugs for the ESDD visit.
- Remain in the study to return for follow-up visits 4 and 12 weeks after the last dose of LDV/SOF, as described in Section 6.4.2.

At the ESDD Visit, any evaluations showing abnormal results indicating that there is a possible or probable causal relationship with the study drugs, should be repeated weekly (or as often as deemed prudent by the Investigator) until the abnormality is resolved, returns to baseline, or is otherwise explained.

The following evaluations are to be completed at the ESDD Visit:

- Review of AEs and changes in concomitant medications
- Complete physical examination (urogenital/anorectal exams will be performed at the discretion of the Investigator)
- Obtain vital signs, including weight
- Obtain 12-lead ECG (performed supine)
- Obtain urine samples for the following laboratory analyses:
 - Urinalysis and urine chemistry
 - Urine pregnancy test (females of childbearing potential only); positive urine pregnancy tests will be confirmed with a serum test.
 - Urine sample storage for possible additional clinical testing
- Obtain blood samples for the following laboratory analyses:
 - Chemistry profile
 - Hematology profile
 - CD4+ cell count
 - Plasma HIV-1 RNA
 - Plasma HCV RNA
 - Plasma storage samples for virology, safety, and/or PK testing

• Obtain estimated glomerular filtration rate according to the Cockcroft-Gault formula (see Section 4.2 for details)

- Complete questionnaires: subject is to read questionnaire by her/himself and write/mark answers directly onto the questionnaires.
 - VAS for HIV adherence
 - HIVTSQc Change version
 - SF-36
 - FACIT-F
 - CLDQ-HCV
 - WPAI: Hepatitis C
- HIV-1 genotype/phenotype resistance testing for subjects with unconfirmed virologic rebound with HIV-1 RNA value ≥ 400 copies/mL.
- Perform study drug accountability:
 - For subjects that **discontinue during Part 1 of the study**, perform study drug accountability on HIV study drugs.
 - For subjects that **discontinue during Part 2 of the study**, perform study drug accountability for HIV and HCV study drugs.
 - If the subject discontinues HCV study drug and is staying on HIV study drug, dispense HIV study drug until the last study visit.
 - If the subject discontinues HIV study drug, HCV study drug will be dispensed at the scheduled visits as described in Section 6.4.1

6.5.2. **30-Day Follow-Up Visit**

Subjects who complete the study through the Post-HCV Treatment Week 12 visit will be required to return to the clinic 30 days after the completion of study for the 30-Day Follow-Up visit.

Subjects who permanently discontinue HIV study drug in Part 1 of the study will be asked to return to the clinic after the completion of the ESDD visit for a 30-Day Follow-Up visit.

 $A \pm 6$ days window may be used to schedule this visit. The following evaluations are to be completed at this visit:

- Review of AEs and changes in concomitant medications
- Perform symptom-directed physical examination

- Obtain vital signs measurement, including weight
- Obtain urine samples for the following laboratory analyses:
 - Urinalysis and urine chemistry
 - Urine pregnancy test (females of childbearing potential only); positive urine pregnancy tests will be confirmed with a serum test.
- Obtain blood samples for the following laboratory analyses:
 - Chemistry profile
 - Hematology profile
 - CD4+ cell count
 - Plasma HIV-1 RNA
 - Plasma HCV RNA

At the 30-Day Follow-Up Visit, any evaluations showing abnormal results indicating that there is a reasonable possibility of a causal relationship with the study drug will be repeated weekly (or as often as deemed prudent by the Investigator) until the abnormality is resolved, returns to baseline, or is otherwise explained.

